The LDL-C retest success threshold was set at 60%. In the atorvastatin AUS, compliance with LDL-C retesting was 6.7% between weeks 2 and 12 and 52% over the course of the study. In the lovastatin AUS, compliance with retesting was 71% over the course of the study ([Pfizer Inc 2016](#), [Melin et al 2004](#)). To better understand the results from these studies, AstraZeneca commissioned AETION® to conduct a study using Prognos Health and IBM MarketScan data to determine the frequency of LDL-C retesting in patients who initiated therapy with a prescription statin (refer to [Appendix D](#)). Of the 1.2M patients in this dataset, 25% had a retest within 3 months, 50% within 6 months and 75% within 12 months. These data suggest that the atorvastatin results are in line with the data from prescription statins while the Merck data was higher and most likely due to their use of an optional Mevacor OTC Self-Management System (MOTC- SMS). While all customers in our program will receive transactional emails to help ensure compliance with retesting, the ultimate impact of these emails is unknown. Therefore, the 60% threshold was set as the minimum value in this study because retesting for Crestor OTC should be at least as good as or better than what is observed currently in the real world with statin therapy.

Secondary endpoints were established to assess compliance with each specific type of DFL warning. For these endpoints, participants will be evaluated for their ability to follow the warnings based on correctly entering the information into the Web App, which would prevent a reorder from occurring, or based on the fact that they stopped therapy (regardless of whether they used the Web App). Since these situations are likely to be low frequency events, no definitive success thresholds were established for these evaluations.

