7 DISCONTINUATION OF STUDY INTERVENTION AND PARTICIPANT DISCONTINUATION/WITHDRAWAL

7.1 Discontinuation of Study Intervention

A participant may decide to permanently discontinue study medication for any reason at any time or the CMOG clinician may decide to permanently discontinue a participant from study medication. If study intervention is permanently discontinued, the participant will be scheduled for a final Virtual Visit to complete all Virtual Visit 2 study procedures or obtain sufficient medical and medication history to determine a final use outcome if all Virtual Visit 2 assessment procedures cannot be completed. See the SoA for data to be collected at Virtual Visit 2.

Note that discontinuation from study intervention is NOT the same thing as a withdrawal from the study.

If a participant decides to permanently discontinue study medication and their last TASS assessment was “OK to Use” or “Ask a Doctor” and indicated the doctor gave them permission to continue treatment, the participant will complete a final TASS at Virtual Visit 2. However, participants will not be required to complete the study mandated LDL-C retest.

While a study participant may decide to discontinue study medication at any time, the only events that would result in study medical personnel instructing the participant to stop taking rosuvastatin are “Stop Use” criteria (which the participant has not self-identified and taken the action to stop use) as listed below:

- Pregnancy
- Severe and unexplained muscle pain, tenderness, or weakness
- Symptoms of liver problems (upper belly pain, dark urine, yellowing of skin or whites of eyes)

If such a situation occurs, the participant's disposition will be classified as "Pregnancy" for this "Stop Use" warning or "Adverse Event" for Severe and unexplained muscle pain, tenderness or weakness or symptoms of liver problems "Stop Use" warnings. The participant will be scheduled for a Virtual Visit 2. All procedures will be performed except a final TASS and a study mandated test for LDL-C.

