9.4.2.2 Secondary Endpoint(s)

Cholesterol Retesting

1 Percentage of participants who are eligible for continuous treatment, and have a cholesterol retest within 6 months of starting medication that was verified at Visit 2 will be calculated as follows:

$$\text{Percentage} = \frac{100^* \text{ (Number of participants who are eligible for continuous treatment and had a cholesterol retest within 6 months after starting medication that was verified at Visit 2)}}{\text{Total number of participants who are eligible for continuous treatment}}$$

The number and percentage of participants who are eligible for continuous treatment and have a cholesterol retest within 6 months of starting medication that was verified at Visit 2 will be summarized by subgroup and overall. Those participants with an unverified cholesterol retest value at Visit 2, and thus required study mandated testing, will not be included in the numerator for this endpoint. The total number of participants who are eligible for continuous treatment will serve as the denominator for the percentages.

The target threshold for this endpoint is that the observed point estimate needs to be at least 60% overall.

Compliance with Stop Use Warning

2 Percentage of participants who correctly self-identify as having a “Stop Use” warning and stop medication, calculated as follows:

$$\text{Percentage} = \frac{100^* \text{ (Number of participants who correctly self-identify as having a “Stop Use” warning and stop medication)}}{\text{Total number of participants who the CMOG clinician identify as having a “Stop Use” warning}}$$

The number and percentage of participants who correctly self-identify as having a “Stop Use” warning and stop medication will be summarized by subgroup and overall.

Compliance with Do Not Use Warning

3 Percentage of participants who correctly self-identify as having a “Do Not Use” warning at the final use assessment, calculated as follows:

$$\text{Percentage} = \frac{100^* \text{ (Number of participants who correctly self-identify as having a “Do Not Use” warning at the final use assessment)}}{\text{Total number of participants who the CMOG clinician identify as having a “Do Not Use” warning}}$$

The number and percentage of participants who correctly self-identify as having a “Do Not Use” warning at final use assessment will be summarized by subgroup and overall.

Compliance with Ask a Doctor Before Use Warning

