3.2.6 Stop Use Warnings

Prior to every drug reorder, participants are required to enter the Web App and take an abbreviated medical reorder assessment. If a participant identifies a "Stop Use" warning, they are instructed by the Web App to both stop use and contact a doctor and will no longer be able to order drug. Stopping use can be ensured through the Web App by preventing participants from reordering medication; however, the participant must take the initiative to contact a doctor.

While the information used to assess stopping use can come from either the Web App or the Targeted Medical and Medication History Form at Virtual Visit 2, the information used to assess contacting a doctor will come from the Targeted Medical and Medication History Form completed by the clinician at Virtual Visit 2.

There are two “Stop Use” warnings for non-prescription rosuvastatin: (1) severe and unexplained muscle pain, tenderness, or weakness and (2) symptoms of liver problems (upper belly pain, dark urine, yellowing of skin or whites of eyes).

While some individuals may identify these symptoms and have treatment stopped through the use of the Web App, there is a reasonable probability that people with these symptoms will simply stop therapy and decide not to use the Web App because they do not want to reorder medication. Meeting the second co-primary endpoint and the secondary endpoint with regard to “Stop Use” warnings requires the participant to identify the “Stop Use” warning on their own. If during the planned 60- and 120-day touchpoint, following review of the eDiary, or through an unplanned contact from the participant, a “Stop Use” criterion is identified, the participants will be managed as follows:

- If during the interview with the clinician, the participant volunteers that they had a “Stop Use Warning”, they will be scheduled for Virtual Visit 2. Participants who self-identify a “Stop Use” criterion will complete all Virtual Visit 2 procedures including a TASS assessment.

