3.2.10 Pill Count

At Virtual Visit 2, all administered pill bottles will be returned, and pill count will be assessed. The total number of pills dispensed is based on the number of 45-day or 90-day supplies ordered through the Web App. The number of pills returned is the total number of pills remaining in each of the returned bottles. For those participants who refuse to send back their pill bottles for a final pill count, the option to count the pills with the study personnel via video conference will be given. For those participants who have lost one or more of their pill bottles, the eDiary data will be utilized to reconcile compliance with dosing.

Because there may be instances in which a participant continues study medication when they should not have (i.e., participant experiences “Stop Use,” “Do Not Use,” or “Ask a Doctor” warning) but does not stop medication, in order to properly assess compliance with continuous dosing, the intended duration of treatment will be used rather than the actual duration of treatment. The intended duration of treatment is as follows:

Intended Duration of Treatment =	(Intended Treatment Stop Date – Date Participant Received First Supply of Study Drug) + 1 Day
----------------------------------	---

where the date of intended treatment stop will be the date when the medication was intended to be stopped (i.e., the date of “Stop Use” warning, the date of the “Do Not Use” warning, the date of the “Ask a Doctor” warning in situations where the participant did not confirm the doctor gave them permission to use the drug, the date of discontinuation or withdrawal, or for participants who did not receive one of the previous outcomes, the date of Visit 2).

Data listings will be provided for participants TASS initial study drug order and their overall study drug accountability.

3.2.11 eDiary

The eDiary will be used to gather minimal and unbiased data on the participant's use of the IP. The information to be gathered will include dosing (date/time and amount of IP taken), adverse

events (changes in health), and medication changes. The participant will record the unique ID from the study drug bottle to confirm receipt of the product.

At the 60-day and 120-day planned telephone contacts, the eDiary will be reviewed to determine if “Stop Use” criteria may be present and to ask about any changes in health.

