The number and percentage of participants who had a cholesterol retest within 6 months of starting medication regardless of final use outcome that was verified at Virtual Visit 2 will be summarized on the AUS ITT population overall and by subgroups (Sensitivity Analysis #1). Those participants with an unverified cholesterol retest value at Visit 2, and thus required study mandated testing, will not be included in the numerator for this endpoint. Participants with multiple retests will be included in the numerator for this endpoint if at least one of the retests is a non-study mandated verified retest. That is, at least one of the retests has a Source Type equal to “Verified source” on the Visit 2 Diagnostic Report. The total number of participants in the AUS ITT population will serve as the denominator for the percentages. There are no target thresholds for this analysis. Another table will be produced with this information based on duration of time in the study (i.e., ≤ 2 months, ≤ 3 months, ≤ 4 months, ≤ 5 months, 6+ months).

An additional analysis to assess the percentage of participants who had a cholesterol retest within 6 months after starting medication that was verified at Visit 2 in the population of participants that reordered medication at least once will be conducted and summarized on the AUS ITT population overall and by subgroups (Sensitivity Analysis #2).

Lastly, an analysis to assess the percentage of participants who had a cholesterol retest within 6 months after starting medication that was verified at Visit 2 in those participants in the AUS ITT population who received at least 3 months of treatment will be conducted and summarized overall and by subgroups (Sensitivity Analysis #3).

Compliance with Stop Use Warning

The percentage of participants who correctly self-identify as having a “Stop Use” warning and stop medication will be calculated as follows:

$$\text{Percentage} = \frac{100^* \text{ (Number of participants who correctly self-identify as having a "Stop Use" warning and stop medication)}}{\text{Total number of participants who CMOG identify as having a "Stop Use" warning}}$$

The number and percentage of participants who correctly self-identify as having a “Stop Use” warning and stop medication will be summarized on the PP population overall and by subgroups.

Compliance with Do Not Use Warning

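### The Stop Use endpoint can take a Web App reorder block as evidence of stopping, although a block does not end dosing from tablets already delivered

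*SAP*

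**What the plan says.** Protocol 9.4.2.2 item 2 defines the endpoint. The numerator is participants who correctly self-identify a Stop Use warning and stop the drug; the denominator is participants in whom the CMOG clinician finds such a warning. The two conditions are joined: "warning and stop medication, calculated as follows". SAP 4.2.3 keeps the same pair: "warning and stop medication will be summarized on the PP population overall and by subgroups".

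SAP 3.2.6 says what may serve as evidence of stopping. It states that "Stopping use can be ensured through the Web App by preventing participants from reordering medication", and that "the information used to assess stopping use can come from either the Web App or the Targeted Medical and Medication History Form" (the clinician fills in this form during the second visit). It expects some participants to "identify these symptoms and have treatment stopped through the use of the Web App". Protocol 3.1 describes the warning endpoints as judged on a correct Web App entry, "which would prevent a reorder from occurring, or based on the fact that they stopped therapy".

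Two other places bear on this. SAP 3.2.10 accepts that "there may be instances in which a participant continues study medication when they should not have", and lists a Stop Use warning among the examples. SAP 3.2.7, on Do Not Use warnings, names the Visit 2 Targeted Medical and Medication History Form as the source for whether the drug was stopped and offers no Web App alternative.

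**The concern.** The reorder block follows automatically once the participant enters the warning. If the block is accepted as evidence of stopping, the second condition is met by the same act as the first. The endpoint then measures identification alone, which is all that the Do Not Use endpoint asks for.

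A block prevents the next shipment. It does not remove tablets already in the home, so a participant can enter the warning, be blocked, and go on taking them. Stopping is the part of this endpoint that matters clinically: Protocol 8.1 treats prompt stopping as critical for Stop Use conditions and regards continued use after a Do Not Use warning as much less risky. As written, the looser evidence rule applies to the more urgent warning.

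**Working it through.** The documents give no target, threshold or expected count for this endpoint, so there is no stated figure to reproduce. The check has three parts.

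**1. Can tablets remain when the block is applied?**

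Inputs: supplies of 45 or 90 tablets; reorder emails at day 25 (45-day supply) and day 45 (90-day supply); reordering opens 5 days after the last delivery (Protocol 6.2 and Section 8, step 19). Assumptions: a single supply, dosing from delivery, shipping time ignored.

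Tablets in hand = tablets supplied − (tablets per day × days since delivery).

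| Moment of reorder assessment | 45-day supply | 90-day supply |
|---|---|---|
| Earliest reorder, one a day | 45 − 5 = 40 | 90 − 5 = 85 |
| Reorder email, one a day | 45 − 25 = 20 | 90 − 45 = 45 |
| Nominal run-out, one a day | 45 − 45 = 0 | 90 − 90 = 0 |
| Reorder email, half use | 45 − 12.5 = 32.5 | 90 − 22.5 = 67.5 |
| Nominal run-out, half use | 45 − 22.5 = 22.5 | 90 − 45 = 45 |

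Half use is the protocol's own example in Section 3.1, where 45 tablets last about 90 days. A daily user who waits until run-out holds none. Anyone who reorders between the earliest date and the email holds 20 to 85 tablets, about 3 to 12 weeks of daily dosing.

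**2. Does any stated rule stop such a participant being credited?**

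- SAP 3.2.6 gives the two sources as alternatives. It does not say which prevails if they disagree.
- Protocol 7.1 and SAP 3.1 deal with warnings that staff detect, those "which the participant has not self-identified and taken the action to stop use". They do not score someone who entered the warning in the app and kept dosing.
- In SAP Appendix B, which governs the final use outcome, the row for a participant who does not stop covers only one who did not identify the warning. No row covers one who identified it and continued.
- The time-to-stop summary in SAP 4.2.4 uses the history form only, but it is restricted to participants already classed as having stopped.

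**3. What is the effect on the percentage?**

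The denominator is fixed by the CMOG clinician. A miscount can only add to the numerator, so the bias is upward. One miscounted participant among n events adds 100/n percentage points. For assumed n of 5, 10 and 20, that is 100/5 = 20, 100/10 = 10 and 100/20 = 5 points.

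**The case against.** The strongest reply is that SAP 3.2.6 names sources and does not set a scoring rule. It says where information can come from, not that a block overrides a form showing continued dosing. The formal numerator still requires stopping, and Protocol 3.1 is a general rationale covering all three warning types, naturally read subject to the specific definition in 9.4.2.2. SAP 3.1 also treats identifying and stopping as separate requirements. A precedence rule may sit in the Coding Process Plan cited in SAP 3.2.3.1, which is not among the documents.

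Part of this stands. A reader might infer that the plan positively scores known continuing dosers as compliant, or that Protocol 3.1 replaces the joint definition. The documents do not support either reading. But SAP 3.2.6 goes beyond naming a source when it says the block can ensure stopping. Read with the either/or rule, it permits credit from the block alone, and an unseen plan cannot be relied on to prevent that.

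The second reply concerns exposure, and it is largely right. A Stop Use entry yields a Do Not Use outcome, the app tells the participant to stop and contact a doctor, and Visit 2 is brought forward, where surplus drug is returned (SAP 3.2.3 and 3.2.6; Protocol Section 8, step 28). Certain reorder answers also trigger an email to the CRO (Protocol 8.4.4). These measures shorten any continued dosing but do not decide how the endpoint is scored.

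The third reply is that a mismatch would show up, because a participant credited without a stop date on the form could not enter the time-to-stop summary. That would help an attentive reader, but it would not correct the reported percentage.

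Using two sources is itself reasonable, since some people will stop without opening the app.

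**Conclusion.** The point holds as a defect in the evidence rule for one secondary endpoint. SAP 3.2.6 and Protocol 3.1 let a reorder block stand as evidence for a condition that the block cannot establish, and the resulting error can only raise the rate.

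Its size is modest. The endpoint is descriptive, Protocol 3.1 sets no threshold and expects few events, and the early Visit 2 limits how long anyone can keep dosing. The documents give neither the number of Stop Use events nor the share who would continue, so no misclassification rate can be stated; the 20, 10 or 5 points per miscounted participant rest on assumed event counts.

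Three stronger readings should be resisted:

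- The tablet counts might be taken as the amount of continued dosing. They are stock in hand that makes continued dosing possible.
- A reader might infer that the 85% test for the final use outcome is affected. That endpoint compares the participant's outcome with the clinician's and does not itself need proof of stopping, so no co-primary result changes.
- A reader might infer that stopping must be credited only within a set number of days. The endpoint has no time limit, and SAP 4.2.4 handles timing as a separate exploratory analysis.

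**What to change.** In SAP 3.2.6 and 4.2.3, and in Protocol 3.1 and 9.4.2.2 item 2:

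- Let the Web App outcome count only for self-identification, and delete the statement that the Web App ensures stopping.
- Credit the stopping part only when the Visit 2 Targeted Medical and Medication History Form confirms that the participant stopped, as SAP 3.2.7 already does for Do Not Use. Handing back drug at Visit 2 should not by itself count as that confirmation. Participants who stop without using the app are credited from the form, as now.
- Use eDiary and pill count as supporting evidence, and report the Web-App-only rate as a supportive line.
- Leave the interval from warning to stopping to the existing time-to-stop summary. No fixed day window is needed.

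The cost is wording in four sections and one derivation from information already collected at Visit 2. The reported percentage may be slightly lower. If the Coding Process Plan already contains this rule, stating it in the SAP is enough.

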3.2.7 Do Not Use Warnings

The “Do Not Use” warnings for non-prescription rosuvastatin are as follows: heart attack, stroke, peripheral artery disease (PAD), an operation or procedure on your heart, liver disease, taking cholesterol-lowering prescriptions medicines, triglyceride lowering prescription medicines, cyclosporine, or warfarin. Prior to every drug reorder, participants are required to enter the Web App and take an abbreviated medical reorder assessment. If the participant identifies they have one of these warnings within the Web App, they will receive a “Do Not Use” outcome.

While one of these criteria could come to the attention of a clinician during the 60- or 120-day touchpoint, following review of the eDiary, or through an unplanned contact from the participant, the clinician will take no action in response to this information. The intent is to determine if participants can identify the “Do Not Use” warnings within the Web App during the reorder process. This is important because consumers will not have clinicians supporting their decisions when the drug is on the market. Consumers must be able to recognize these warnings on their own or identify them through the Web App so that the medication is stopped. The information regarding whether a participant stopped the medication will come from the Targeted Medical and Medication History Form completed by the clinician at Virtual Visit 2. This approach is appropriate in this study because the likelihood of harm to the participant from continuing therapy is very low. Note that Crestor 5 mg is an indicated dose for the treatment of heart attack, stroke, PAD, those with an operation or procedure on the heart or for those on cyclosporine or warfarin. While concomitant use with other statins is not a recommended treatment approach, use of Crestor with other cholesterol or triglyceride lowering medications is a common treatment approach and can be safely done with Crestor 5 mg.

It is possible that during the 60- or 120-day touchpoint or through an unplanned contact, the participant informs the clinician that they believe they met a “Do Not Use” criterion for which they stopped use of the medication and have no intention of restarting medication. If this occurs, the clinician will make no determination, but will schedule Virtual Visit 2. At Virtual Visit 2, all procedures will be performed, including a final use assessment in the Web App.

If the participant refuses to schedule a Virtual Visit 2, the clinician will attempt to obtain medical and medication history to determine if the participant experienced a “Do Not Use” warning. If

the clinician confirms the “Do Not Use” warning, the participant will have met the Do Not Use endpoints. If not, they have failed the Do Not Use endpoints.

See [Appendix B](#) for additional details on how the participant’s final use outcome would be assessed based on these different scenarios.

